5.2.2 Secondary Efficacy Outcomes

5.2.2.1 Investigator's Assessment of Clinical Response

The investigator will make an assessment of Clinical Response at the EOT and PTE visits, based on the definitions below. The secondary efficacy outcome is the overall assessment of clinical response at PTE (derived from the investigator assessments at the EOT and PTE visits) in the mITT and CE-PTE populations as defined in [Table 2](#).

5.2.2.1.1 EOT Visit

At the EOT visit (on the day of or within 2 days following the last dose of test article), the investigator will indicate the clinical status of the infection under study as detailed below.

Clinical Success at the EOT assessment will be defined as meeting the following:

- The subject is alive
- The infection is sufficiently resolved such that further antibacterial therapy is not needed. These subjects may have some residual changes related to infection requiring ancillary (ie, non-antibiotic) treatment, eg, bandages on a healing wound, debridement of uninfected tissue (ie, necrotic)

Clinical Failure will be defined as meeting any of the criteria below:

- Investigator discontinued test article and indicated that the infection had responded inadequately such that alternative (rescue) antibacterial therapy was needed
- The subject received antibacterial therapy that may be effective for the infection under study for a different infection from the one under study
- The subject developed an AE that required discontinuation of test article prior to completion of the planned test article regimen and alternative (rescue) antibacterial therapy was needed
- Unplanned major surgical intervention (ie, procedures that would not normally be performed at the bedside) for the infection under study
- The subject died before evaluation

- Other specified reason as indicated on the eCRF.

Indeterminate The clinical response to test article could not be adequately inferred:

- The subject was not seen for EOT assessment because they withdrew consent, were lost to follow-up, or other specified reason
- Other specified reason

5.2.2.1.2 PTE Visit

At the PTE Visit (7 to 14 days after the subject's last day of study therapy) the investigator will indicate one of the following outcomes relating to the primary infection under study:

Clinical Success at the Post Therapy Evaluation assessment will be defined as meeting the following:

- The subject is alive
- The infection is sufficiently resolved such that further antibacterial therapy is not needed. These subjects may have some residual changes related to infection requiring ancillary (ie, non-antibiotic) treatment, eg, bandages on a healing wound, debridement of uninfected tissue (ie, necrotic)

Clinical Failure will be defined as meeting any of the criteria below:

- The infection required additional treatment with alternative (rescue) antibacterial therapy
- The subject received antibacterial therapy between EOT and PTE that may be effective for the infection under study for a different infection from the one under study
- Unplanned major surgical intervention (ie, procedures that would not normally be performed at the bedside) for the infection under study between EOT and PTE
- The subject died before evaluation
- Other specified reason

Indeterminate The clinical response to test article could not be adequately inferred:

- The subject was not seen for PTE assessment because they withdrew consent, were lost to follow-up, or other specified reason
- Other specified reason

Overall Clinical Response at PTE (based on the investigator's assessment) is determined as follows ([Table 2](#)) from the investigator's assessments at the EOT and PTE Visits:

Table 2. Investigator's Assessment of Clinical Response

EOT Visit	PTE Visit	Overall Assessment of Clinical Response at PTE Visit
Success	Success	Success
Success	Failure	Failure
Success	Indeterminate	Indeterminate
Failure	Success	Failure
Failure	Failure	Failure
Failure	Indeterminate	Failure
Indeterminate	Success	Indeterminate
Indeterminate	Failure	Failure
Indeterminate	Indeterminate	Indeterminate

EOT = end of treatment; PTE = post-therapy evaluation.

For the mITT population, the proportion of mITT subjects with a Clinical Success is defined using the following formula (where the denominator adds to the total number of subjects in the mITT population):

$$\frac{\text{Number of subjects with Clinical Success}}{(\text{Number of subjects with Clinical Success} + \text{Number of subjects with a Clinical Failure} + \text{Number of subjects with an Indeterminate response})}$$

By definition, subjects in the CE-EOT and CE-PTE populations cannot have an Indeterminate response. Thus, for the CE-EOT and CE-PTE populations, the proportion of subjects with a Clinical Success is defined using the following formula:

$$\frac{\text{Number of subjects with Clinical Success}}{(\text{Number of subjects with Clinical Success} + \text{Number of subjects with a Clinical Failure})}$$

5.2.2.2 Microbiologic Outcomes

Microbiological response definitions for the evaluations performed at the EOT and PTE Visits and analyzed in the micro-mITT and ME populations are presented in Table 3 below. At the EOT and/or PTE visit, infection site specimen cultures and Gram stains should be obtained only for subjects who are clinical failures and require alternative antibacterial treatment for the infection under study.

If a subject has the same pathogen (ie, same genus and species) identified from both an ABSSSI and blood specimen, a microbiological response is determined for each of the pathogens. For tables summarizing microbiologic response for pathogens from the ABSSSI or blood specimen, if the same pathogen is isolated from both an ABSSSI and blood specimen, the worst response is summarized. The microbiologic response for the ABSSSI pathogen is based on the pathogen isolated from the EOT or PTE specimen, if a specimen was collected. The microbiologic response for the blood pathogen is based on the blood sample collected at EOT or PTE, or if a sample was not collected at the post-baseline visit, the blood sample collected prior to and closest to the visit.

Table 3. Per-Pathogen Microbiological Response Definitions at the EOT and PTE Visits

Term	Definition
Eradication	Absence of original baseline pathogen
Presumed Eradication	No source specimen to culture in a subject assessed with a clinical success by the Investigator
Persistence	Continued presence of the original baseline pathogen
Presumed Persistence	No source specimen to culture in a subject assessed with a clinical failure by the Investigator
Indeterminate	The subject's clinical response is indeterminate or other circumstance that precludes a microbiological evaluation

EOT = end of treatment; PTE = post-therapy evaluation.

Microbiological outcomes are further categorized as favorable, unfavorable and indeterminate. Favorable microbiological outcomes are defined as eradication or presumed eradication. Unfavorable microbiological outcomes are defined as persistence or presumed persistence. Microbiological response will be derived using electronic microbiology data from the central laboratory (or local laboratory if central data are not available) and from pathogen determination provided by the sponsor for each baseline isolate.

Overall microbiological response at PTE is determined as follows ([Table 4](#)) from the microbiological responses at the EOT and PTE Visits:

Table 4. Per-Pathogen Microbiologic Response

EOT Visit	PTE Visit	Overall Microbiologic Response at PTE
Favorable	Favorable	Favorable
Favorable	Unfavorable	Unfavorable
Favorable	Indeterminate	Indeterminate
Unfavorable	Favorable	Unfavorable
Unfavorable	Unfavorable	Unfavorable
Unfavorable	Indeterminate	Unfavorable
Indeterminate	Favorable	Indeterminate
Indeterminate	Unfavorable	Unfavorable
Indeterminate	Indeterminate	Indeterminate

Note: Favorable is defined as eradication or presumed eradication. Unfavorable is defined as persistence or presumed persistence.

EOT = end of treatment; PTE = post-therapy evaluation.

Per-subject responses will be based on per-pathogen outcomes. To have an overall per-subject favorable microbiologic response, the outcome for each baseline pathogen must be favorable (eradicated or presumed eradicated). If the outcome for any pathogen is unfavorable (persistence or presumed persistence), the subject will be considered to have an unfavorable per-subject microbiologic response. Subjects with an indeterminate response for all pathogens will be considered to have an indeterminate per-subject microbiologic response. If the same pathogen is isolated from both the blood and the ABSSSI site culture, the worst outcome will be used to determine per-subject microbiologic response. Superinfections will not be considered in the microbiological response. Microbiological response from worst to best are as follows: persistence, presumed persistence, indeterminate, presumed eradication and eradication.

The overall per-subject microbiologic response at PTE is determined from the per-subject microbiologic responses at the EOT and PTE Visits as follows ([Table 5](#)):

Table 5. Per-Subject Microbiologic Response

EOT Visit	PTE Visit	Overall Microbiologic Response at PTE
Favorable	Favorable 
 • Eradication • Presumed Eradication 	Favorable 
 • Eradication • Presumed Eradication
Favorable	Unfavorable 
 • Persistence • Presumed Persistence 	Unfavorable 
 • Persistence • Presumed Persistence
Favorable	Indeterminate	Indeterminate
Unfavorable 
 • Persistence • Presumed Persistence 	Favorable	Unfavorable 
 • Persistence • Presumed Persistence
Unfavorable 
 • Persistence • Presumed Persistence 	Unfavorable 
 • Persistence • Presumed Persistence 	Unfavorable 
 • Persistence • Presumed Persistence
Unfavorable 
 • Persistence • Presumed Persistence 	Indeterminate	Unfavorable 
 • Persistence • Presumed Persistence
Indeterminate	Favorable	Indeterminate
Indeterminate	Unfavorable 
 • Persistence • Presumed Persistence 	Unfavorable 
 • Persistence • Presumed Persistence
Indeterminate	Indeterminate	Indeterminate

Note: Favorable is defined as eradication or presumed eradication. Unfavorable is defined as persistence or presumed persistence.

EOT = end of treatment; PTE = post-therapy evaluation.

For the microbiological modified intent to treat (micro-mITT) population, the proportion of subjects with a favorable microbiological response is defined using the following formula (where the denominator adds to the total number of subjects in the micro-mITT population):

$$\frac{\text{Number of subjects with eradication} + \text{Number of subjects with presumed eradication}}{\text{Number of subjects with eradication} + \text{Number of subjects with presumed eradication} + \text{Number of subjects with persistence} + \text{Number of subjects with presumed persistence} + \text{Number of subjects with indeterminate response}}$$

By definition, the microbiological evaluable (ME) populations (ME-EOT and ME-PTE) must have sufficient information to determine the outcome and thus, excludes subjects with indeterminate responses. For the ME analysis set, the proportion of subjects with a microbiological response is defined using the following formula:

$$\frac{\text{Number of subjects with eradication} + \text{Number of subjects with presumed eradication}}{\text{Number of subjects with eradication} + \text{Number of subjects with presumed eradication} + \text{Number of subjects with persistence} + \text{Number of subjects with presumed persistence}}$$

Microbiological response definitions of superinfection and new infection are presented in Table 6 below:

Table 6. Microbiological Response Definitions: Superinfection or New Infection

Term	Definition
Superinfection	Isolation of a non-baseline ABSSSI pathogen from the primary ABSSSI site or blood while the subject is on test article (ie, during test article administration, Day 1 to EOT) and the subject has worsening or new signs or symptoms of the primary ABSSSI (ie, the subject is deemed a clinical failure by the investigator)
New infection	Isolation of a non-baseline ABSSSI pathogen from a post-treatment (ie, after EOT) culture from the primary ABSSSI site or blood in a subject with worsening or new signs or symptoms of the primary ABSSSI (ie, the subject is deemed a clinical failure by the investigator)

ABSSSI = acute bacterial skin and skin structure infection.

For subjects with multiple microbiological samples taken either during test article administration (for determination of superinfection) or after test article administration (for determination of new infection) all cultures will be used in the analysis.

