- ⁿ Blood pressure and pulse rate should be measured within 30 min before, and approximately (\pm 15 minutes) 1 hour after and 3 hours after the completion of the odd numbered doses on Days 2 and 3. In the event that the subject takes the dose before arriving for the office visit, the site should collect the 1 and 3 hour post dose measurements if possible, if not then a single measurement should be made at any time during the visit and the date and time recorded.
- ^o A 12-lead ECG should be performed at screening, at the EOT visit, and as otherwise clinically indicated.
- ^p A urine dipstick test will be performed locally at Screening.
- ^q All women will have a local urine or serum pregnancy test at Screening.
- ^r All women will have blood collected for a serum β -hCG pregnancy test at the Central Laboratory at the Screening, EOT and PTE visits.
- ^s Blood will be collected for hematology (includes coagulation) and serum chemistry testing at the Central Laboratory at Screening and at the Day 3, Day 7, Day 10, EOT and PTE visits.
- ^t At the Screening visit, blood will be collected for local laboratory hematology and serum chemistry evaluations required for assessing subject eligibility.
- ^u If bacteria are isolated from blood cultures, repeat blood cultures should be collected. If subsequent blood cultures are also positive, repeat the blood cultures as necessary until negative blood cultures are obtained.
- ^v At the EOT and/or PTE visit, blood cultures and infection site specimen cultures and Gram stains should be obtained only for subjects who are clinical failures and require alternative antibacterial treatment for the infection under study.
- ^w A subject's AEs and SAEs will be recorded and reported from signing of the ICF to the Final Follow-up assessment.
- ^x A 6 hour fast is required before and a 2 hour fast is required following all odd numbered doses. The total duration of test article therapy for all subjects will be 7 to 14 days. Test article may be dispensed and reconciled by blinded personnel. Subjects will be asked to return all unused test article and packaging at each visit. At the EOT visit subjects will return the test article packaging and site staff will perform accountability.
- ^y Subjects should receive their first dose of test article at the site within 4 hours after randomization.
- ^z Subjects should be instructed not to take the odd numbered dose on Day 2 until they return to the site for the Day 2 visit.

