17.3 Microbiological Assessment of the Site of Infection

At the Screening visit, material should be collected from the site of infection and submitted to site's local microbiology laboratory for Gram stain and culture. The type of specimen submitted will be recorded on source documents at the microbiology laboratory. Laboratory reports on Gram stains should include a semi-quantitative description of the number of polymorphonuclear leukocytes per low power field (ie, 100×) and a description of bacteria seen.

It is critical, especially at Screening, that the best possible specimen be obtained.

As the site of infection responds to therapy, repeated cultures may not be clinically appropriate and/or there may be no material for culture. At the EOT and/or PTE visit, infection site specimen cultures and Gram stains should be obtained only for subjects who are clinical failures and require alternative antibacterial treatment for the infection under study.

The following types of specimens are considered acceptable in order of preference⁶:

- biopsy of involved cutaneous or subcutaneous tissue, preferably from the advancing margin of the lesion;
- debrided tissue;
- tissue scraping (using curette or scalpel);
- needle aspirate of involved, nonpurulent cutaneous or subcutaneous tissue;
- pus or infected tissue collected during an incision and drainage procedure;
- pus aspirated into a syringe;
- deep swab of purulent material (only if collected from infected tissue that has been incised or is draining).

Surface swabs of wounds, inflamed skin, or drainage (including purulent material) are not acceptable and should not be submitted. For subjects with cellulitis/erysipelas, a skin/subcutaneous tissue punch biopsy at the ‘leading edge’ (not the center) of the involved area is preferred. If this cannot be done, a needle aspirate of the ‘leading edge’ of the cellulitic area should be performed.

All specimens submitted to the site’s local laboratory are to be evaluated for aerobic and, where appropriate, anaerobic culture. Culture results are to include a semi-quantitative description of the organisms on the primary culture plate and identification of all isolates to the level of genus and species. Susceptibility testing for linezolid can be performed locally using a standard method chosen by the laboratory. Results of this testing can be used by investigators along with clinical findings to help guide therapy.

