 - Subjects will be defined as an Indeterminate if the investigator cannot determine whether the subject is a Clinical Success or Failure at the EOT or PTE Visits or the subject has a missing response. By definition, subjects with an Indeterminate response are included in the denominator for analyses in the mITT and micro-mITT populations, and thus, are considered Clinical Failures. Subjects with an Indeterminate response are excluded from the CE-EOT, CE-PTE, ME-EOT and ME-PTE populations.

- For microbiologic response:
 - If no source specimen is obtained and the subject has an investigator's assessment of Clinical Response, the per-pathogen microbiological response is based on the investigator's assessment of Clinical Response (ie, the response is a presumed response). A per-pathogen microbiological response at the EOT Visit or PTE Visit will be considered Indeterminate only if the Clinical Response at EOT or PTE is also Indeterminate.
- Missing values for other individual data points will remain as missing. Missing values will not be imputed and only observed values will be used in data analyses and presentations.
- Where individual data points are missing, categorical data will be summarized based on reduced denominators (ie, only subjects with available data will be included in the denominators).

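### SAP Table 3 lets a site culture taken after rescue antibacterials have started count as Eradication, so a rescued relapse can be coded microbiologically Favorable

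*SAP*

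**What the plan says.** SAP section 5.2.2.2 sets the per-pathogen coding. For the infection site it says "The microbiologic response for the ABSSSI pathogen is based on the pathogen isolated from the EOT or PTE specimen, if a specimen was collected". Table 3 defines Eradication as "Absence of original baseline pathogen" and adds nothing about when the specimen was taken relative to rescue. Presumed Persistence is "No source specimen to culture in a subject assessed with a clinical failure by the Investigator". The grouping is then: "Favorable microbiological outcomes are defined as eradication or presumed eradication".

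On who is sampled at EOT and PTE, the Protocol flowchart (section 8, footnote v) says that cultures "should be obtained only for subjects who are clinical failures and require alternative antibacterial treatment for the infection under study". Protocol section 17.3 and SAP section 5.2.2.2 repeat the rule. None of these places says whether the sample is to come before or after the start of the alternative drug.

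Two statements bear on whether such a culture could be set aside. Table 3 makes a response Indeterminate if the clinical response is indeterminate, and also under a residual clause for any other situation that prevents microbiological evaluation. SAP section 8.3 says "A per-pathogen microbiological response at the EOT Visit or PTE Visit will be considered Indeterminate only if the Clinical Response" is also Indeterminate. That sentence stands in a bullet that opens with the case where no source specimen was obtained.

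**The concern.** The subjects cultured at EOT and PTE are those who need another antibacterial. Some may already be taking it by the time of the visit. Protocol section 13.2 leaves further treatment to the investigator or the subject's own health care provider, and PTE falls 7 to 14 days after the last dose, so rescue can begin well before the PTE specimen. A culture that no longer grows the baseline pathogen may then reflect the rescue drug. Read as written, Table 3 still codes it as Eradication in the randomized arm.

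Two subjects with the same clinical course can thus get opposite microbiologic results depending only on whether a specimen was taken during rescue. At stake are the per-subject and per-pathogen favorable rates in the micro-mITT and ME populations, which SAP section 10.4 presents as support for the clinical findings.

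**Working it through.** The plan gives no figure on this point, so the check follows its coding rules: SAP Table 3 at each visit, then Table 4 (Table 5 per subject) to combine visits, with Table 2 for the overall clinical result.

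| EOT clinical / site specimen | PTE clinical / site specimen | EOT code | PTE code | Overall microbiologic | Overall clinical |
|---|---|---|---|---|---|
| Success / none | Success / none | Presumed Eradication | Presumed Eradication | Favorable | Success |
| Success / none | Failure / none | Presumed Eradication | Presumed Persistence | Unfavorable | Failure |
| Success / none | Failure / pathogen grown | Presumed Eradication | Persistence | Unfavorable | Failure |
| Success / none | Failure / pathogen absent | Presumed Eradication | Eradication | **Favorable** | Failure |
| Failure / none or grown | any | Presumed Persistence or Persistence | any | Unfavorable | Failure |
| Failure / pathogen absent | Success / none | Eradication | Presumed Eradication | **Favorable** | Failure |
| Failure / pathogen absent | Failure / pathogen absent | Eradication | Eradication | **Favorable** | Failure |
| Failure / pathogen absent | Failure / none or grown | Eradication | Presumed Persistence or Persistence | Unfavorable | Failure |

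The second and fourth rows are the point: the same relapse after EOT success is Unfavorable without a specimen and Favorable with one that lacks the pathogen. If that specimen predates rescue, Eradication is a fair code. If it was taken on rescue, the result says little about the test article, yet the table does not separate the two.

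**Conditions.** Overall Favorable at PTE needs Favorable at EOT. Per subject, every baseline pathogen must be favorable, and if the same pathogen was in blood and at the site, the worse response is used (SAP 5.2.2.2).

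**Effect of the Indeterminate clause.** If Table 3's residual clause were applied at PTE, Favorable plus Indeterminate gives Indeterminate in Table 4. SAP section 10.4 tabulates that as unfavorable in micro-mITT; the ME populations exclude it. One subject could therefore be Favorable, unfavorable or excluded, depending on which sentence is followed.

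**Populations.** SAP section 8.6 uses PTE data in mITT whenever the visit occurs, and micro-mITT is a subset of mITT. SAP section 6.1.5.3 does not exclude a subject from CE merely for rescue given for insufficient effect, so ME-PTE can be affected too.

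**Scale, illustration only.** Each recoded subject moves an arm's favorable rate by 100/n points, where n is the micro-mITT size per arm. The documents do not give n. The ceiling is 704/2 = 352; 150 is an assumed low value.
- One subject: 100/352 = 0.28 points; 100/150 = 0.67 points.
- Five subjects: 500/352 = 1.42 points; 500/150 = 3.33 points.

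**After the fix.** The fourth row, when the specimen was taken on rescue, becomes Presumed Persistence and Unfavorable, matching the second row.

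**The case against.** The strongest reply is that Table 3 already has an outlet: its residual Indeterminate clause could take in a culture made uninformative by rescue. A reader might infer that SAP section 8.3 closes that outlet, because it allows Indeterminate only with an Indeterminate clinical response. The text does not firmly support this, since the sentence sits in a bullet about missing specimens. So the outlet may be open. It does not name post-rescue cultures, however, and it sits uneasily with section 8.3. What remains is a rule that gives Favorable when read literally and an exception that may or may not apply.

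A second reply is that the case is narrow. A decision to stop test article itself prompts the EOT evaluation (Protocol 14.3.1.2), which limits rescue before the EOT culture. Protocol section 17.3 rejects surface swabs and notes that a responding site may yield nothing to culture, so some rescued subjects will have no valid specimen and will already be Presumed Persistence. This stands, and it limits the number affected, but it does not remove the case.

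A third reply is that the endpoint carries little weight. Microbiologic outcomes appear under the secondary heading of SAP section 5.2.2, but SAP section 10.4 and Protocol section 22.6 analyze them as additional variables, with descriptive intervals and no non-inferiority conclusion. This also stands.

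**Conclusion.** The gap is real and minor. Literal use of Table 3 codes a rescued relapse as Favorable when the PTE culture lacks the baseline pathogen, under the conditions shown above. A narrower EOT version exists because EOT may fall up to 2 days after the last dose.

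Three stronger readings are tempting, and the documents do not support them.
- A reader might infer that the main efficacy results are inflated. They are not: Early Clinical Response does not use these cultures, and a relapse needing rescue is a Clinical Failure in the investigator's assessment at PTE.
- A reader might infer false disagreement in the clinical-microbiologic concordance table. SAP section 10.4 specifies that table at EOT, where the relapsing subject is a Success with Presumed Eradication, so the two agree. Only the EOT path could disturb it.
- A reader might infer that the treatment difference is pulled toward zero by a known amount. The documents give no rate of rescue before the visit or of cultures taken on rescue, and unequal culturing or rescue timing between arms could move the difference either way. Size and direction are unknown; the per-subject arithmetic is only a scale.

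**What to change.** Add one rule to SAP Table 3 and section 8.3. A specimen collected after the first dose of rescue, or of any other potentially effective non-study antibacterial, and not growing the baseline pathogen does not count as Eradication; its response is assigned from the clinical response as if no specimen were available, which is Presumed Persistence for a clinical failure. Growth of the baseline pathogen in such a specimen remains Persistence. In the same edit, align Table 3's residual Indeterminate clause with the sentence in section 8.3, so that one rule governs. Indeterminate would be a defensible alternative code; what matters is that one is chosen and written down before unblinding.

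The cost is a sentence and a comparison of two dates in the programming, with a convention for same-day ties. SAP section 8.3 already has missing antibiotic start times queried, and SAP Table 6 already separates on-treatment from post-treatment cultures, so specimen dates are needed anyway. No procedure or clinical management changes. The downside is that favorable rates become slightly lower.
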